For each patient, the period for notification of adverse events begins from the time when the patient receives the first dose of the study medication or from the date when the patient gives his/her informed consent if he/she has already been exposed to the study medication, and it ends at the end of the observation phase of the study, which is a minimum of 28 calendar days after the last administration of the study medication; the process for declaring the different types of adverse events to the Pfizer/Novartis Pharmacovigilance departments or approved representative during this period are listed in table 4 above. If the patient receives the study medication on the last day of the observation phase, the notification period will be extended by 28 calendar days after the end of the observation phase. Usually, the date when the consent form is signed will correspond to the date that the patient is enrolled in the study.

In some cases, they may be a delay between the date that the consent form is signed and the date of enrolment in the study.

In cases in which the patient gives his/her consent but is never enrolled in the study (for example: the patient changes his/her mind about participating; does not meet the screening criteria), the notification period ends on the date when the decision is made not to include the patient.

If the investigator becomes aware of a serious adverse event occurring at any time after the end of the observation phase that he/she considers to be related to a study medication, this serious adverse event must also be declared to the Pharmacovigilance department at Pfizer.

If an SAE, non-serious AE or specific scenario occurs after the end of the observation phase, it only needs to be declared to the pharmacovigilance department at Novartis, by fax or by e-mail, if the investigator suspects a causal link with the study medication(s).

Assessing causality

The investigator must assess causality and report on it. The investigator must obtain sufficient information to determine the causality of every adverse event. For AE considered to be related to a study medication, the investigator must monitor these events until resolution or stabilisation of the event and/or of any sequelae to the extent deemed to be acceptable by the investigator, and with the approval of Pfizer/Novartis of this assessment.

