It is important to note that statistical comparisons in the strictest sense between the different treatment groups in this observational study are not appropriate due to the expected bias and because the groups are not comparable at enrolment (treatments not assigned randomly). If, however, comparisons are envisaged, a multivariate Cox model will be used in order to adjust for patient characteristics that may potentially be associated with the type of treatment received and survival and that could be liable to skew the estimates (confounding factors, effect modification).

 Safety of the treatments (targeted therapies and other treatments) during the prospective phase of the study, defined by instances of treatment discontinuation and the reasons for this, adverse events (graded according to the 'Common Terminology Criteria for Adverse Events' (CTCAE) version 4.0 of May 2009), and any complications of adverse events.

The proportion of patients for whom adverse events are reported (total proportion and proportion reporting grades 3 or 4 adverse events) will be estimated as well as the proportion who stop treatment due to an inability to tolerate it.

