5.7. Safety

Safety assessment criteria will be used to:

- Treatment discontinuations and reasons for this,
- Adverse events and any complications recorded prospectively (graded according to the 'Common Terminology Criteria for Adverse Events' (CTCAE) version 4.0, dated May 2009).

These criteria will be shown descriptively in the safety analysis set.

The analyses of adverse events will be performed twice on the safety analysis set:

- by treatment group at inclusion;
- by group in which treatment was received at least once during the study. In this analysis, the AE will be attributed to ongoing treatment at the start of the AE. An AE beginning after a treatment was discontinued could be attributed to the treatment depending on the rules shown in the table below.

Prior to the safety analysis, the number of patients who received the treatment at least once in the group (targeted therapy/other treatments) and in the treatment subgroups will also be presented. Exposure for each treatment group and subgroup will be calculated.

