5.7.1. Treatment Drop-outs and Documented Reasons for Dropping Out of the Study

The following parameters will be presented for each of the analysis groups (targeted therapy or other treatment) and for each treatment:

- Total duration of exposure since starting treatment (also shown for the reference set).
- Numbers and percentages of patients who had at least one documented discontinuation of treatment in the study. The results will be shown for incident patients, prevalent patients and then for all patients.
- Number of documented temporary discontinuations by patient in the study.

- Time to the first temporary discontinuation from inclusion into the study. The results will be shown for incident patients, prevalent patients and then for all patients.
- Reasons for temporary discontinuations.
- Durations of temporary discontinuations.
- Numbers and percentages of patients who discontinued treatment permanently.
- Time until permanent discontinuation from inclusion into the study. The results will be shown for incident patients, prevalent patients and then for all patients.
- Time until permanent discontinuation from inclusion. Results will be shown for incident patients, prevalent patients and then for all patients.
- Reason for permanent discontinuation.

The analyses of exposure to treatment will be described by treatment received at inclusion but also by treatment received at least once during the study (main treatment or as a combination). If the patient takes the same treatment on several occasions over different periods, the sum of the exposure periods will be calculated.

The analyses of temporary discontinuations will be described by main treatment received at inclusion but also by main treatment ongoing at the time of temporary discontinuation.

In addition, the total duration of exposure of the treatment at inclusion since it was started will be analysed by the ECOG index value at inclusion.

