5.7.2. Adverse Events

The numbers and percentages of patients with the following characteristics will be shown overall, and by group at inclusion during the study (targeted therapy/other treatments). We will also show the results by treatment being received at the time of inclusion and during the study: everolimus/sunitinib/chemotherapy/somatostatin analogs etc.

- at least one adverse event,
- at least one serious adverse event,
- at least one adverse event with a suspected relationship with the study treatment,
- an adverse event which was fatal,
- at least one adverse event resulting in permanent discontinuation of treatment,
- at least one adverse event resulting in dosage adjustment/temporary discontinuation of treatment.

- at least one adverse event with a suspected relationship with the study treatment leading to permanent discontinuation of the treatment,
- at least one adverse event with a suspected relationship with the study treatment leading to a dosage adjustment/temporary discontinuation of treatment,
- at least one serious adverse event with a suspected relationship with the study treatment leading to permanent discontinuation of the treatment,
- at least one serious adverse event with a suspected relationship with the study treatment leading to a dosage adjustment/temporary discontinuation of treatment.

The same information will be produced for grade ≥ 3 adverse events.

The following information will also be shown:

- at least one grade 3 adverse event,
- at least one grade 3 serious adverse event,
- at least one grade 3 adverse event with a suspected relationship with the study treatment,
- at least serious grade 3 adverse event with a suspected relationship with the study treatment,
- at least one grade 4 or higher adverse event,
- at least one grade 4 or higher adverse event with a suspected relationship with the study treatment.

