The adverse events will also be described by treatment group, in patients who received treatment at least once during the study (targeted therapies/other treatments; the other treatments will also be described depending on whether these involved chemotherapy/somatostatin analogs/others) by System Organ Class (SOC) and Preferred Term (PT). The same analysis will be presented for adverse events with a suspected relationship with the study treatment, grade 3 adverse events with a suspected relationship with the study treatment, serious grade 3 adverse events with a suspected relationship with the study treatment, adverse events grade =3, adverse events ≥4, for serious adverse events, non-serious adverse events, serious grade =3 adverse events, adverse events which resulted in temporary discontinuation of treatment, adverse events which resulted in permanent discontinuation of treatment and adverse events which resulted in the death of patient.

In terms of the analysis by treatment received during the study, several rules have been defined:

The denominator will be the number of patients who received the ongoing treatment during the prospective period at least once. In the case of combination treatments, the treatments will be separated and the patient will be counted several times.

The AE will be deemed to be on treatment until 28 days after the treatment is stopped. Similarly, if the investigator links an AE to a treatment, this will also be counted on this related treatment (regardless of the dates the treatment is taken).

If the treatment is still ongoing at the time of last news, the AE will be deemed to be on treatment for up to 28 days after the date of last news.

Amongst the "other" treatments, Lutathera treatment will be deemed to be metabolic radiotherapy.

If the date of onset of the adverse event is missing:

- If the day of the event is missing, the event will be attributed to all treatments received during the month when the AE was declared.
- if the day and month of the event are missing, the event will be attributed to all treatments during the year in which the AE is declared unless the treatment was received after the end of the AE.

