NB: the listings will show the retrospective adverse events and the prospective adverse events, whereas the summary tables will only include the prospective adverse events.

The listing of adverse events reported in patients excluded from the safety analysis set will be provided where applicable.

Handling of missing data:

If the seriousness (serious/non-serious) and/or causality with the treatment are missing, the most adverse situation for treatment is assumed in the summary tables, i.e. a serious case and/or one related to the study treatment.

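### Adverse event percentages are not adjusted for time at risk, and the exposure reported with them starts at first dose while tabulated events start at inclusion; the distortion can go either way

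*SAP*

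**What the plan says.** Safety is part of the primary objective (SAP 5.5). Protocol 8.3.2.1 sets the measure: "The proportion of patients for whom adverse events are reported (total proportion and proportion reporting grades 3 or 4 adverse events) will be estimated". SAP 5.7.2 follows it: "The numbers and percentages of patients with the following characteristics will be shown overall, and by group at inclusion during the study". Tables 14.3.2.1 and 14.3.2.2 add the number of events to each row. No rate per unit of time and no time-to-first-event analysis is planned.

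For the analysis by treatment received during the study, SAP 5.7.2 states "The denominator will be the number of patients who received the ongoing treatment during the prospective period at least once". The window depends on the row:

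- **Any event, serious event, fatal event:** actual exposure plus 28 days ("The AE will be deemed to be on treatment until 28 days after the treatment is stopped").
- **Events leading to a stop or dose change:** actual exposure only.
- **Related events:** the causality column, whatever the treatment dates.

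For the analysis by treatment at inclusion, the SAP states no on-drug window.

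The listings hold retrospective and prospective events, "whereas the summary tables will only include the prospective adverse events". This matches the notification period in Protocol section 7, which starts "from the date when the patient gives his/her informed consent if he/she has already been exposed to the study medication".

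On exposure, SAP 5.7 says "Exposure for each treatment group and subgroup will be calculated". Exposure is defined in SAP 4.7 as last receipt minus first receipt plus one day. SAP 5.7.1 presents it as "Total duration of exposure since starting treatment (also shown for the reference set"). It appears in Tables 14.3.1.1 to 14.3.1.4, apart from the adverse event tables, and nothing cuts it at inclusion.

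**The concern.** A patient who stays on a drug longer after inclusion has more time in which a first event can be counted. Two treatments with the same event rate can therefore show different percentages.

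The natural remedy for a reader is to look at the exposure tables. For a prevalent patient, those include months before inclusion whose events are kept out of the summary tables. Anyone who relates the events to that exposure divides by time in which no event could count.

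The SAP accepts the underlying principle for survival. SAP 6.1.3 says prevalent patients are at risk only from inclusion, and SAP 5.5.1 left-truncates progression-free and overall survival for that reason. The safety part of the same objective makes no such allowance. At stake is how the adverse event columns, printed side by side by treatment, will be read.

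**Working it through.** The plan states no event rate, no time on drug by treatment and no share of prevalent patients, so it has no figure of its own to reproduce. All rates and durations below are assumptions chosen to show direction and rough size.

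**1. Crude percentage under one common rate.** With a constant rate *r* of first events, the percentage is 1 − exp(−*r* × *t*), where *t* = (post-inclusion months × 30.4375 + 28) / 365.25 years. The 28 days come from SAP 5.7.2.

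| Post-inclusion months | *t* (years) | *r* = 0.3 per year | *r* = 0.6 per year |
|---|---|---|---|
| 6 | 0.577 | 16% | 29% |
| 12 | 1.077 | 28% | 48% |
| 24 | 2.077 | 46% | 71% |

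Longer post-inclusion use alone raises the percentage.

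**2. Events divided by the displayed exposure.** Counting events over the post-inclusion months and dividing by all months since first dose gives post / (pre + post) of the true rate (28-day tail ignored):

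- 3 months before, 6 after: 6/9 = 0.67
- 12 before, 12 after: 12/24 = 0.50
- 12 before, 6 after: 6/18 = 0.33

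Here long pre-inclusion use makes a drug look less toxic.

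**3. Both effects on the same drugs.** Take 5 events per 100 patient-months (0.6 per year) for every drug.

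| Months before + after inclusion | Crude percentage | Events per 100 displayed patient-months | Events per 100 post-inclusion patient-months |
|---|---|---|---|
| 0 + 6 | 29.2% | 5.0 | 5.0 |
| 12 + 18 | 61.2% | 5 × 18/30 = 3.0 | 5.0 |
| 18 + 6 | 29.2% | 5 × 6/24 = 1.25 | 5.0 |

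The second drug looks worse than the first by percentage and better by displayed exposure. The third row shows that pre-inclusion use does not raise the percentage at all. Only the aligned rate is the same for all three.

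**4. Early toxicity.** Suppose the hazard is 0.20 per month for the first 3 months and 0.02 after that (28-day tail ignored).

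- Incident patients followed 12 months: cumulative hazard 3 × 0.20 + 9 × 0.02 = 0.78, so 1 − exp(−0.78) = 54.2%.
- Prevalent patients, 12 months before and 12 after inclusion: 12 × 0.02 = 0.24, so 1 − exp(−0.24) = 21.3%.

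The early events of prevalent patients fall before inclusion and are not tabulated. This again makes a drug with many prevalent users look safer.

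**The case against.** The strongest reply is that the study is descriptive. Protocol 8.3.2.1 prespecifies proportions and calls strict comparison between treatment groups inappropriate, and Protocol 9.4 describes each group independently. Nothing in the SAP divides events by exposure or offers exposure as a correction, so the mismatch affects a calculation that the plan does not make.

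Other displays also help. Event counts accompany the percentages. Table 14.3.1.7 gives time from inclusion to permanent discontinuation, split by incident and prevalent status. Table 14.1.4.1.11 shows time between treatment start and inclusion for prevalent patients. Table 14.3.1.3, unlike 14.3.1.1, is not titled as running from treatment start, so its pre-inclusion content is inferred from the general formula in SAP 4.7.

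Much of this stands. The percentages meet the stated descriptive aim, and the pre-inclusion time is not hidden. It does not close the gap:

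- Time to permanent discontinuation needs a stop date, which patients still on drug lack, and it covers only the treatment at inclusion. Time at risk cannot be summed from it.
- The adverse event tables have no incident/prevalent split.
- Within a single group, a percentage over a window of unstated average length is still hard to interpret.

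A reader might infer that longer-used drugs will look more toxic. The documents do not support that as a general conclusion. It follows only for crude percentages when post-inclusion time is longer; steps 2 and 4 push the other way, and the net direction is not fixed.

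**Conclusion.** The point holds as one of adjustment and alignment. The percentages in Tables 14.3.2.1 and 14.3.2.2 take no account of time at risk, and for prevalent patients the displayed exposure and the tabulated events cover different periods. The bias may go in either direction.

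The sizes rest on assumed values: 29%, 48% and 71% for 6, 12 and 24 months at 0.6 per patient-year, and about half the true rate for 12 months before and 12 after inclusion. Unequal time on drug is itself plausible rather than stated. Exposure classes run from 0–3 to over 24 months, and the case report form lists a reached cumulative dose and a scheduled stop as reasons for stopping, but no duration is given for any treatment. The plus-28-day window applies only to some rows of the analysis by treatment received.

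A reader might also infer that the safety results cannot be used across groups at all. That goes too far: the percentages remain valid descriptions, and what is missing is a companion measure on a matched time base. This is a cheap improvement, not a flaw that undoes the safety analysis.

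**What to change.** Keep the percentages and event counts, and add the following to Tables 14.3.2.1 and 14.3.2.2.

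- **Main rows (any event, serious event, grade 3 event):** patients with an event per 100 patient-years, with 95% confidence interval. Time at risk runs from the later of inclusion and first dose to the earliest of first event, stop plus 28 days, and last news. Count only events inside that window; SAP 5.7.2 would otherwise also accept events up to 28 days after last news.
- **Events leading to permanent stop:** actual exposure without the 28 days, as the SAP 5.7.2 table already has it.
- **Related events:** restrict the rate to events inside the window, or give no rate, because SAP 5.7.2 counts these whatever the treatment dates.
- **Split:** show rates overall and by incident and prevalent status. A pooled rate would hide the effect in step 4.
- **Exposure:** report prospective time at risk beside the adverse event tables. Keep total exposure since treatment start as a separate description.
- **Footnotes:** combination dates are approximated from visits, and the SAP's own note to Table 14.3.1.3 says that exposure to combinations is overestimated. Partial onset dates need imputing for a time to first event.

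The cost is a few derived columns, since SAP section 8 lists the main-treatment start and stop dates among the key data. The downside is that a single rate assumes a roughly constant hazard, which is why the percentages stay.

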5.7.1. Treatment Drop-outs and Documented Reasons for Dropping Out of the Study

The following parameters will be presented for each of the analysis groups (targeted therapy or other treatment) and for each treatment:

- Total duration of exposure since starting treatment (also shown for the reference set).
- Numbers and percentages of patients who had at least one documented discontinuation of treatment in the study. The results will be shown for incident patients, prevalent patients and then for all patients.
- Number of documented temporary discontinuations by patient in the study.

- Time to the first temporary discontinuation from inclusion into the study. The results will be shown for incident patients, prevalent patients and then for all patients.
- Reasons for temporary discontinuations.
- Durations of temporary discontinuations.
- Numbers and percentages of patients who discontinued treatment permanently.
- Time until permanent discontinuation from inclusion into the study. The results will be shown for incident patients, prevalent patients and then for all patients.
- Time until permanent discontinuation from inclusion. Results will be shown for incident patients, prevalent patients and then for all patients.
- Reason for permanent discontinuation.

The analyses of exposure to treatment will be described by treatment received at inclusion but also by treatment received at least once during the study (main treatment or as a combination). If the patient takes the same treatment on several occasions over different periods, the sum of the exposure periods will be calculated.

The analyses of temporary discontinuations will be described by main treatment received at inclusion but also by main treatment ongoing at the time of temporary discontinuation.

In addition, the total duration of exposure of the treatment at inclusion since it was started will be analysed by the ECOG index value at inclusion.

